#### Recruitment of Provider Participants:

We will collect qualitative interviews with 20 VA mental health providers who work with Veterans with schizophrenia to inform feasibility and implementation.

Study staff will attend individual clinic team meetings, and will introduce the study during the clinic meetings. Providers will be asked if they would like to participate in the study/qualitative interviews at that time. If providers express an interest in participating, they will be contacted by study staff to schedule a time to review the consent form. Providers may also self-identify for participation in the study if they hear about the study and are interested.

### Payment to Participants

#### Veteran Participant payments:

Schizophrenia participants will be paid \$30 for completing each of the three study assessments at baseline (prior to starting the intervention), post treatment (immediately following the intervention) and follow-up (3 months following the intervention), for a maximum total of \$90 for the assessments. They will also be paid \$10 for completing each of the 2 individual sessions, and \$5 for each of the 24 group sessions for a maximum total of \$140 for individual/group sessions. If a veteran is found to be ineligible after completing the baseline's diagnostic interview, he or she will be paid \$5 and his or her study participation will be complete.

Participants will be paid at the completion of each research appointment. If study staff encounter a problem with accessing vouchers or gift cards (for example if the fiscal year budget does not allow for access to research funds) and are unable to pay participants at the time of their completed appointment, study staff will pay the participant as soon as possible (when funds become available) following their appointment if paid in VA voucher or gift card. If vouchers or gift cards are unavailable, the participant may be offered cash. Participants can also be mailed the voucher or gift card for their convenience. Participants will be informed ahead of time if there will be any delay in payment for completing research tasks and offered payment in cash.

#### Provider Participant payments:

VA provider participants will not be paid for their participation in this study.

## **5.3 Informed Consent Procedures**

### Schizophrenia Participants:

Written informed consent will be secured from all participants. Our research staff are carefully trained on obtaining consent from participants with serious mental illness and supervised by senior staff members. Only study staff listed on this protocol will be allowed to obtain informed consent for this study. Approval will be secured from the mental health clinician before a potential participant is approached, and the study staff will verify that any potential participant is sufficiently stabilized to provide consent before approaching him/her. After securing clinician approval, the study interviewer will meet the participant, introduce him/herself to the participant, and inform that participant that their clinician has been contacted about their participation in our research. The study interviewer will use the clinician's name so the participant will not be confused. The study interviewer will then provide an overview of the project, and invite him/her

to participate. Interested participants are provided an informed consent form. Staff members are trained to recognize symptoms of severe mental illness and cognitive impairment that could undermine a participant's ability to provide informed consent. The consent form is reviewed with all participants in detail. All participants will be given the opportunity to read the entire consent form on their own and to ask the research staff member questions prior to agreeing to participate and prior to signing the form. Research staff are trained in strategies for interacting with people with severe and persistent mental illness, including speaking slowly and clearly, stopping to summarize frequently, and providing time for questions.

After the consent form has been summarized in detail with the participant and all questions answered, the staff confirms that the participant is still interested in participating by soliciting a verbal response. Those who express willingness to provide consent must complete a brief questionnaire to assess competency and understanding of the consent form. If the participant is unable to answer the questions correctly, staff re-reviews the aspects of the study that the participant did not understand. The staff member asks the questions a second time. If the participant cannot answer all questions correctly, he/she will not be enrolled in the study.

Per IRB regulations, a copy of the signed consent form is given to the participant, and the original is kept in the research office. Participants will also receive a Health Insurance Portability and Accountability Act Authorization to Obtain, Use and Disclose Protected Health Information for Research (HIPAA) that will be summarized for them. Staff will ask participants if they have any questions once the document has been read, and then participants will sign the authorization. A copy of this signed form will be given to the participant. In keeping with the requirements put forth in the Department of Veterans Affairs: a) social security numbers of veterans will not be solicited; b) research staff will restrict telephone and other contacts with veterans to the procedures and data elements outlined in the IRB approved protocol; c) initial contact with veterans must be made in person or by letter prior to telephone contact; d) verification of the study will be provided following the guidelines set forth in HRPP/IRB policies and procedures 10G. In following the most recent VHA Handbook, version 1200.5, consents will no longer be scanned nor will study enrollment or progress notes be added into participants' medical records.

#### Provider Participants:

Written informed consent will be secured from all provider participants. Our research staff are carefully trained on obtaining consent from participants and are supervised by senior staff members. A member of the study staff will meet the participant, introduce him/herself to the participant, and then provide an overview of the project, inviting him/her to participate. Interested participants are provided an informed consent form. The consent form is reviewed with all participants in detail. After the consent form has been reviewed and all questions answered, the staff confirms that the participant is still interested in participating by soliciting a verbal response. Per IRB regulations, a copy of the signed consent form is given to the participant and the original is kept in the research office.

## **5.4 Inclusion/Exclusion Criteria**

#### Schizophrenia Participants:

## Training Trial

**Inclusion criteria:** (1) DSM diagnosis of schizophrenia or schizoaffective disorder; (2) Age between 18 and 75 years; (3) Seen by a mental health professional at the recruitment site at least once every 3 months for the last 6 months (to demonstrate that participants receive ongoing and regular mental health care); (4) Competent to sign Informed Consent. **Exclusion criteria:** (1) Documented history of serious neurological disorder or head trauma with loss of consciousness; (2) Mental retardation (defined as a total IQ score less than 70 as measured by the Wechsler Test of Adult Reading or as indicated by chart review; (3) Inability to effectively participate in the baseline assessments due to psychiatric symptoms on two successive appointments; (4) Current problematic substance use as indexed by scores on the Michigan Alcoholism Screening Test and the Drug Abuse Screening Test (described below); (5) Currently meet criteria for a major depressive episode.

## RCT

**Inclusion criteria:** (1) DSM diagnosis of schizophrenia or schizoaffective disorder; (2) A CAINS minimum rating of a "moderately severe deficit" (3 or greater on a 0-4 scale) on one or more of any symptom domain within the affect-motivation factor (i.e., symptoms of asociality, avolition, and anhedonia) or a minimum rating of a "moderate deficit" (2 or greater on a 0-4 scale) on two or more of any affect-motivation symptom domain; (3) Age between 18 and 75 years; (4) Seen by a service provider twice within the last 6 months *or once in the last 6 months consistently for two years, as in line with the Veteran's recorded mental health treatment plan* (to demonstrate that participants receive ongoing and regular mental health care); (5) Competent to sign Informed Consent. **Exclusion criteria:** (1) Documented history of serious neurological disorder; (2) Mental retardation (defined as a total IQ score less than 70 as measured by the Wechsler Test of Adult Reading or as indicated by chart review; (3) Inability to effectively participate in the baseline assessments due to psychiatric symptoms on two successive appointments; (4) Current problematic substance use as indexed by scores on the Michigan Alcoholism Screening Test and the Drug Abuse Screening Test (described below).

## Provider Participants:

**Inclusion criteria:** (1) Work in VA mental health service in one of the 3 study locations (Baltimore, Perry Point, Washington DC VAMCs), (2) Work with Veterans with schizophrenia, (3) Willingness to participate. **Exclusion criteria:** (1) None.

## **5.5 Study Evaluations**

Table 3 Domain	Measure (time for administration)	Time-point
-------------------	-----------------------------------	------------

Diagnosis	Structured Clinical Interview for DSM-IV  - Mood Disorders and Psychotic Symptoms Sections (SCID)(60 minutes)	BL
Symptoms	Clinical Assessment Interview for Negative Symptoms  (CAINS); Brief Psychiatric Rating Scale (24-item version)  (BPRS)(60 minutes)	BL, PT, FU
Social/Community Functioning Recovery/Self-efficacy	Role Functioning Scale (RFS); Social Functioning Scale (SFS);  Brief University of California San Diego Performance-based Skills Assessment (UPSA)  Maryland Assessment of Recovery Survey (MARS)  Community Reintegration of Service Members Computer Adaptive Test  (CRIS-CAT); Quality of Life (TL-30S) (20 minutes)	BL, PT, FU
Attitudes/Beliefs	Success and Resource Appraisals Questionnaire Dysfunctional Attitudes Scale (DAS I and II)  Future Thinking Task  (15 minutes)	BL, PT, FU
Attendance/Satisfaction	Participant Satisfaction Questionnaire and Service Satisfaction Scale  Qualitative interview (10 minutes)	PT, FU
Feasibility/Acceptability	Recruitment and retention of participants, Attendance and participation data, Information from qualitative interviews from Veterans and providers, EnCoRE interventionist logs and supervision notes	Ongoing Qualitative Interviews: PT
Adherence and Competence	Adherence Rating Scale, Competence Rating Scale; Completed by blinded coders.	Ongoing
Substance Abuse	Michigan Alcoholism Screening Test  , Drug Abuse Screening Test  (5 minutes)	BL,
Cognitive functioning	Weschler Test of Adult Reading, Brief Cognitive Assessment (15 minutes)	BL,
Other	Demographics Form, Clinic Services Use Tracking Form (CSUTF), Morisky Medication Index  , Medication Use, Service Use Form (SUF)  (10 minutes)	BL, PT, FU

## 5.6 Data Analysis

Data will be screened for errors using frequency and contingency tables and univariate and bivariate plots before analysis. As the primary outcome measures are scales we expect (but will verify) that they are approximately normally distributed; if not, we will consider alternatives (e.g. transformation or a generalized linear model). Our primary analytical approach will be to compare EnCoRE versus control at post-treatment (Hypotheses 1 thru 4 below) after adjusting for BL scores. This is one type of analysis of covariance (ANCOVA) linear regression model that improves power by reducing residual variation. We will also check whether there is an interaction between baseline severity and treatment effect. If there is, we will report these results as well. We will conduct a similar analysis (adjusting for BL) to compare the conditions at FU while including the post-treatment assessment in a repeated measures model, as including these values can help reduce bias in the FU estimates when participants miss the FU but are assessed at PT. We will enter site as a fixed effect into the analysis models because there will only be 3 sites (in relatively close proximity). Because the groups will have rolling admission, we do not expect significant group effects, however we will verify this by calculating intra-group correlations (i.e. ICC's) and if model fit is improved, we will include group as a random effect in

primary analysis models (then, the model would be a linear mixed model that includes adjustment for BL). In this case we will replace site with group in the model as sample size will not be sufficient to adjust for both. Viewed from another perspective, group is nested within site and is thus the more specific nested variable to be adjusted for. We will also check covariate balance (demographics, clinical characteristics) across the two conditions. Randomization should keep the two conditions in balance, however it is possible for imbalance to occur by chance. If a substantively relevant BL covariate significantly differs across the two conditions we will adjust for the covariate. Because this is a randomized trial, no covariates other than BL score of the outcome measure and site will be adjusted for a priori. To assess potential bias due to missing assessments, we will compare BL characteristics of participants who were versus were not assessed at PT/FU. We will check that attrition rates are comparable in the two conditions. Our procedures and analyses will be based on the intent-to-treat principle: we will attempt to assess all participants at PT and FU including those who discontinue treatment early. All available data will be included in the analyses. We expect to have assessments on 85% of the sample (i.e. 15% attrition) at PT and 80% (i.e. 20% attrition) at FU. To analytically address potential bias in the comparison of the conditions at PT due to missing assessments, we will conduct a sensitivity analysis by imputing missing outcome values using a regression multiple imputation approach that will produce unbiased estimates under the Missing at Random (MAR) assumption, similar to mixed effects models. If Non-Ignorable (NI) dropout is indicated we will further conduct a sensitivity analysis under departures from the MAR assumption using the procedure of Carpenter. SAS Procedures MI and MIAnalyze will be used. Similar procedures will be used for missing data at FU.

Specific Aim 1: Train therapists and refine the EnCoRE manual in a trial with approximately 6 Veterans with schizophrenia. Procedures are described in section 3C.

Specific Aim 2: Conduct a randomized controlled trial to test the efficacy of EnCoRE in producing positive changes at PT and FU on the primary outcomes of negative symptoms and social and community functioning. Hypothesis 1 (H1): Veterans exposed to EnCoRE will have lower mean scores than those in the control condition on the affective-motivational deficit subscale of the CAINS at post-treatment. The EnCoRE group will continue to have a lower mean than the control group at FU (secondary hypothesis). . Letting Y1, Y2, and Y3 be values for the motivational deficit subscale of the CAINS at BL, PT, and FU respectively, and Tx condition the treatment indicator (Tx condition=1, if EnCoRE; Tx=0 if control condition), the analysis model for Hypothesis 1 (post-treatment) will be:  $Y_2 = Y_1 + \text{Site (or Group)} + \text{Tx condition} + \text{error}$  (ANCOVA). Substantively relevant BL covariates found to significantly differ between treatment conditions, even after randomization, would be added. We will also check if there is a covariate by treatment interaction in this case. Significance test of the Tx condition coefficient will test hypothesis 1. The analysis model for the comparison at FU will be similar, but will include Y2 and Y3 as repeated responses and include a random effect to account for correlation between the two. Thus, it will be a linear mixed model with adjustment for BL (Y2 and Y3 repeated response and adjustment for Y1). A time and group-by-time interaction term will be added (time indicating FU versus PT) in order to estimate the difference of means at FU assessment. A specified contrast using the mixed model will test the hypothesis that the mean affective-motivational deficit in the EnCoRE condition will continue to be less than in the control

condition. Hypothesis 2 (H2): Veterans exposed to EnCoRE will have a higher mean score than controls at post-treatment on the RFS and SFS. The EnCoRE group will continue to have higher a mean score than control at the 3 month FU. The analysis model for H2 will be parallel to those for H1.

Specific Aim 3: Examine qualitative interviews completed by (1) Veterans who participated in EnCoRE and (2) Mental Health Providers who work with Veterans with schizophrenia to determine aspects of EnCoRE that were perceived as more or less helpful, interesting, and valuable in order to make adjustments prior to conducting a larger, multi-site implementation trial. Qualitative data analyses will be organized and supervised by [name]. Interviews with Veterans randomized to EnCoRE (n=49) and mental health providers who work with Veterans with schizophrenia in PRRCs (n=10) will be audiotaped and transcribed by a trained HIPAA compliant professional. We will analyze data in 3 phases employing “constant comparison” of data units with others and data with emerging themes. Transcripts will be: (1) read and discussed by the PI and Co-I, creating a brief summary that captures our best understanding of what the interviewee sought to convey; (2) closely open-coded (categorizing each line or small unit of data with labels that convey their meaning vis-a-vis the study focus) by 2 team members, and these codes discussed to consensus. Breaking the data into small units and not using an a priori code template helps keep analysis focused on the data and the interviewee’s meaning, minimizing tendencies to see data through one’s preconceived ideas about the topics at hand; (3) As these steps near completion, we will examine meaning across interviews via focused cross-interview coding to organize themes, variations and interrelationships among the ideas, views, and experiences conveyed by the multiple interviews. We will pay particular attention to ideas/themes that can contribute to intervention effectiveness and implementation. In doing so we will consider interviewee’s personal reflections distinct from their observations/impressions of other Veterans, and will pay close attention to their personal theories regarding the nature, causes, structure, meaning, effects, and management of negative symptoms. Qualitative software program Atlas-ti 5.0 will be used. The study team will discuss the results to identify concrete ideas for improving/refining the intervention suggested by each point in the combined summaries. The results of (2) will also be used by the study team to identify issues related to feasibility and implementation.

Secondary Aim 1: Test the efficacy of EnCoRE in producing positive changes at PT and FU on a second measure of social/community functioning (UPSA-B). Hypothesis 3 (H3): Veterans exposed to EnCoRE will have higher mean scores than controls at post-treatment and at FU on the UPSA-B total score.

Secondary Aim 2: Test the efficacy of EnCoRE in producing positive changes at PT and FU on mental health recovery. Hypothesis 4 (H4). Veterans exposed to EnCoRE will have higher mean ratings on the MARS than control at PT and FU. Analysis models for H4 will be parallel to those for H1.

Secondary Aim 3: Assess the modifying effect of covariates on the effectiveness of EnCoRE including general cognitive ability and psychotic symptoms. Hypothesis 5 (H5): General cognitive ability and symptoms of psychosis will not impact the effectiveness of the intervention

for negative symptoms and community functioning at PT and FU (See analysis below for H6). Hypothesis 6 (H6): Greater ratings of consumer participation in and satisfaction with the intervention will be associated with better PT and FU outcomes. For each of the potential modifiers in H5 and H6, we will re-fit the primary analysis model for PT outcomes after adding two terms, the potential modifier and the interaction term between the treatment condition indicator (Tx condition) and the potential modifier. The variable will be a modifier if the coefficient for the interaction term is statistically significant ( $p$ -value<.05). A similar model will be used to assess modification at FU but there will be additional interaction terms with time (including 3-way interaction time\*treatment condition\*modifier), in order to estimate modifying effects at FU (i.e. separate effects at FU vs. PT).

Secondary Aim 4: Examine the associations of improvements in attitudes/beliefs regarding success and recovery on symptoms and functioning. Hypothesis 7 (H7): Improvements on ratings of attitudes/beliefs (e.g. DBS, FTT score) in the EnCoRE condition from BL to PT and FU will be positively associated with improvements in symptom and functioning outcome measures from BL to PT and FU, respectively. Change scores will be computed for attitudes/beliefs and recovery, and for symptom and functioning scales. Pearson correlations will be calculated and significance tests of the null hypothesis of zero correlation will be conducted. Note: These tests of association can be conducted even if improvement on ratings of self-efficacy and recovery are not significant in H3.

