### Hypotheses

Hypothesis 1 (H1): Veterans exposed to EnCoRE will have lower mean scores than those in the control condition on the affective-motivational deficit subscale of the CAINS at post-treatment. The EnCoRE group will continue to have a lower mean than the control group at FU (secondary hypothesis). . Letting Y1, Y2, and Y3 be values for the motivational deficit subscale of the CAINS at BL, PT, and FU respectively, and Tx condition the treatment indicator (Tx condition=1, if EnCoRE; Tx=0 if control condition), the analysis model for Hypothesis 1 (post-treatment) will be:  $Y_2 = Y_1 + \text{Site (or Group)} + \text{Tx condition} + \text{error}$  (ANCOVA). Substantively relevant BL covariates found to significantly differ between treatment conditions, even after randomization, would be added. We will also check if there is a covariate by treatment interaction in this case. Significance test of the Tx condition coefficient will test hypothesis 1. The analysis model for the

comparison at FU will be similar, but will include Y2 and Y3 as repeated responses and include a random effect to account for correlation between the two. Thus, it will be a linear mixed model with adjustment for BL (Y2 and Y3 repeated response and adjustment for Y1). A time and group-by-time interaction term will be added (time indicating FU versus PT) in order to estimate the difference of means at FU assessment. A specified contrast using the mixed model will test the hypothesis that the mean affective-motivational deficit in the EnCoRE condition will continue to be less than in the control condition.

Hypothesis 2 (H2): Veterans exposed to EnCoRE will have a higher mean score than controls at post-treatment on the SFS and RFS. The EnCoRE group will continue to have higher a mean score than control at the 3 month FU. The analysis model for H2 will be parallel to those for H1.

Hypothesis 3 (H3): Veterans exposed to EnCoRE will have higher mean scores than controls at post-treatment and at FU on the UPSA-B total score.

Hypothesis 4 (H4). Veterans exposed to EnCoRE will have higher mean ratings on the MARS than control at PT and FU. Analysis models for H4 will be parallel to those for H1.

Hypothesis 5 (H5): General cognitive ability and symptoms of psychosis will not impact the effectiveness of the intervention for negative symptoms and community functioning at PT and FU (See analysis below for H6).

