Hypothesis 6 (H6): Greater ratings of consumer participation in and satisfaction with the intervention will be associated with better PT and FU outcomes. For each of the potential modifiers in H5 and H6, we will re-fit the primary analysis model for PT outcomes after adding two terms, the potential modifier and the interaction term between the treatment condition indicator (Tx condition) and the potential modifier. The variable will be a modifier if the coefficient for the interaction term is statistically significant (p-value<.05). A similar model will be used to assess modification at FU but there will be additional interaction terms with time (including 3-way interaction time\*treatment condition\*modifier), in order to estimate modifying effects at FU (i.e. separate effects at FU vs. PT).

Hypothesis 7 (H7): Improvements on ratings of attitudes/beliefs (e.g. DBS, FTT score) in the EnCoRE condition from BL to PT and FU will be positively associated with improvements in symptom and functioning outcome measures from BL to PT and FU, respectively. Change scores will be computed for attitudes/beliefs and recovery, and for symptom and functioning scales. Pearson correlations will be calculated and significance tests of the null hypothesis of zero correlation will be conducted. Note: These tests of association can be conducted even if improvement on ratings of self-efficacy and recovery are not significant in H3.

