
Statistical Test of Hypothesis: The analysis of the primary outcomes utilized a mixed effects model accounting for a random therapy group effects and the analysis included all available data at baseline, post-treatment, and follow-up time-points. Error terms across time points were assumed correlated with unstructured correlation matrix. To test time-specific hypotheses, terms in the mean model included separate indicators for post-treatment and follow-up time points, and interaction terms between these indicators and condition. Based on randomization to treatment condition, the model assumed no differences at baseline, i.e. any differences were assumed to be due to random sampling error. All continuous outcome scales were checked for skew, and an appropriate transformation was applied as needed. Statistical significance was defined as $p \leq .05$. All analyses were performed using SAS version 9.4. In moderator analyses we examined whether treatment effects on the primary outcomes (CAINS MAP, SFS) differed according to baseline dysfunctional attitudes measured by the DAS and SARA-Q. We also examined whether baseline negative symptoms (CAINS MAP) modified treatment effects for the SFS. Each moderator variable was dichotomized at the median. In separate models, the moderator and interaction terms with the moderator were added to the primary linear mixed effects models to test whether treatment effects at post-treatment and follow-up time points differed for those above versus below the median.

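### The baseline-severity by treatment check is committed to the report only if an interaction is found, and the SAP lists no such check on CAINS-MAP itself

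*Protocol*

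**What the plan says.** Protocol section 5.6, just after describing the ANCOVA that adjusts the post-treatment comparison for baseline score, adds: "We will also check whether there is an interaction between baseline severity and treatment effect". The next sentence carries the only reporting commitment: "If there is, we will report these results as well". Neither sentence names an outcome, a severity scale, a time point or a criterion for deciding that an interaction is present. A criterion of p below .05 on the interaction coefficient does appear in the protocol, but only for H5 and H6 (Hypotheses, and Secondary Aim 3 in section 5.6).

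The SAP, under Statistical Test of Hypothesis, lists the moderator analyses. It looks at whether "treatment effects on the primary outcomes (CAINS MAP, SFS) differed according to baseline dysfunctional attitudes measured by the DAS and SARA-Q". It then adds: "We also examined whether baseline negative symptoms (CAINS MAP) modified treatment effects for the SFS". On form it says: "Each moderator variable was dichotomized at the median". It lists no test of baseline CAINS-MAP on CAINS-MAP and none of baseline SFS on SFS. It neither explains this nor repeats the protocol's reporting condition. Its primary model includes the baseline scores among the responses: "the model assumed no differences at baseline, i.e. any differences were assumed to be due to random sampling error".

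Two further facts give the check its interest. Entry to the RCT (section 5.4) requires minimum CAINS ratings in the affect-motivation domains, and CAINS-MAP is the first primary outcome in the SAP's outcomes table.

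**The concern.** The protocol makes the check unconditional but the report conditional on the result. An estimate that appears only when it is large enough to count as an interaction is a selected estimate, and a trial sized for a main effect has little power for an interaction. Small and imprecise results would go unseen, and modest interactions that did surface would be overstated on average.

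The SAP adds a second gap. For a trial that selects Veterans on negative-symptom severity, it is natural to ask whether benefit on the negative-symptom outcome varies over the severity range admitted. The SAP's list does not cover that, so a reader of the SAP cannot tell whether the CAINS-MAP check was run and showed nothing or was not run. What is at stake is the credibility of one exploratory statement about who benefits, not the main result.

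**Working it through.** **Inputs.** From Sample Size Considerations: d = .50, alpha = .025 (taken as two-sided; the protocol does not say), power .80, 15% attrition at post-treatment, and a baseline to post-treatment correlation r of .70, then .63. Allocation is equal (Randomization Procedures). The documents give no figure for any interaction test.

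**Step 1: reproduce the plan's N.** For ANCOVA, n per arm = 2(1 − r²)(z₁ + z₂)²/d², with (z₁ + z₂)² = (2.241 + 0.842)² ≈ 9.505.
- r = .70: 2 × .51 × 9.505/.25 = 38.8 per arm. The total of 77.6, divided by .85, is 91.2, so N = 92 as stated.
- r = .63: 2 × .6031 × 9.505/.25 = 45.9 per arm. The total of 91.7, divided by .85, is 107.9, so N = 108 as stated. (Rounding up to 46 per arm first gives 109, a rounding difference only.)

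The stated inputs therefore describe the design the plan had in mind.

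**Step 2: precision of the interaction.** Assessed at post-treatment: 108 × .85 = 91.8, about 46 per arm. With baseline and outcome in SD units, each arm's slope has variance (1 − r²)/n. The difference in slopes has

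SE = √[2(1 − .63²)/46] = √(1.2062/46) = .162 SD of outcome per SD of baseline.

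This is a normal approximation; a direct ANCOVA simulation with 46 per arm gave .167. An estimate must exceed 1.96 × .162 = .32 to reach p<.05, and 80% power requires (1.96 + 0.84) × .162 = .45. On the second figure, with an average effect of .50, the effect would be .95 for someone 1 SD above the baseline mean and .05 for someone 1 SD below.

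**Step 3: effect of reporting only when p<.05.** Two million normal draws for each assumed true value, keeping only the significant ones:

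| True interaction (SD per SD, assumed) | Share of trials reporting it | Mean absolute estimate when reported | Ratio to truth | Wrong sign among those reported |
|---|---|---|---|---|
| 0 | 5% | .38 | – | 50% |
| .10 | 9.5% | .39 | 3.9 | 5% |
| .15 | 15% | .40 | 2.7 | 1% |
| .25 | 34% | .43 | 1.7 | 0.1% |
| .50 | 87% | .54 | 1.1 | 0% |

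The inflation is large for modest interactions and nearly vanishes for large ones.

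**Step 4: the SAP's median split.** With the same 92 people, the difference in treatment effect between the two halves has SE = √[.6031 × 4/23] = .32 SD. That needs about .91 SD for 80% power, well above the .50 the trial was sized to detect overall.

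**Step 5: the two documents side by side.** The protocol's check refers to baseline severity without naming an outcome; from its position it most naturally belongs to the ANCOVA of each outcome on its own baseline. The SAP carries a severity moderator across to SFS only. The SAP's method adds the moderator to its mixed model. For CAINS-MAP that would mean moderating a response vector that already contains the moderator, a difficulty that does not arise when baseline CAINS-MAP moderates SFS.

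**The case against.** The strongest reply is that the sentence in section 5.6 follows directly on the ANCOVA and may be no more than the usual check for parallel baseline slopes, with interaction results shown in addition to the main result. Nothing says that a null result will be withheld. That is fair: conditional reporting is the natural reading, not an express rule of suppression. It still leaves no commitment to report a null.

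Four stronger inferences are tempting, and the documents do not support them.
- *Everything published about who benefits is filtered by its result.* The condition attaches to one check. H5 ("General cognitive ability and symptoms of psychosis will not impact the effectiveness of the intervention"), H6 and the SAP's DAS, SARA-Q and SFS moderators carry no such condition.
- *The SAP left out the CAINS-MAP check because of what it showed.* The SAP is dated April 2021 and written in the past tense, so this cannot be excluded, but nothing shows it. The baseline-as-response model offers a structural explanation, although the SAP does not state that one either.
- *Any interaction shown will be exaggerated.* The inflation is an average over significant results; at a true value of .50 it is only about 1.1 times.
- *The protocol alone leaves a checked null indistinguishable from no check.* Under the protocol the check is always done, so silence would mean that none was found. The ambiguity comes from the SAP.

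It also stands that the p<.05 trigger is borrowed from H5 and H6, that the protocol names no outcome, and that even full reporting would give a wide interval.

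**Conclusion.** The point holds in a limited form. For one exploratory check, the protocol commits to a report only if an interaction is found, and the SAP lists no baseline CAINS-MAP check on CAINS-MAP and does not say why. Followed literally, this yields a selected estimate from a low-power test. With about 46 assessed per arm and r = .63, a true interaction of .10 to .25 SD per SD would be reported in roughly 10% to 34% of trials, at about 3.9 to 1.7 times its size.

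These figures rest on three assumptions: that found means p<.05, that the planning values for attrition and correlation hold, and that true interactions lie in the range shown, for which the documents give no guide. The primary comparison, alpha and N are unaffected. The change is worth making because it removes the selection at almost no cost, not because the main conclusion is at risk.

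**What to change.** Replace the conditional sentence in section 5.6 with wording such as: *The baseline score by condition interaction will be estimated for CAINS-MAP and for SFS at post-treatment and follow-up, with baseline continuous, and reported with its 95% CI whatever the p-value. These analyses are exploratory.*

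Fit it in the protocol's own ANCOVA form (Y2 and Y3 on Y1), with the time interactions needed for the follow-up estimate, because the SAP's model uses baseline as a response. Add the CAINS-MAP check to the SAP on the same terms, and state there why it was not listed. If results are already written up, the estimates can be added as a reporting note.

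The cost is a few extra models on data already collected, with no change to sample size or alpha. The intervals will be wide, about ±.32 SD per SD of baseline at post-treatment on the planning figures, and the text should say so.
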